#### Study Procedures: Randomized Controlled Trial

To achieve Aim 2, we will conduct a pilot RCT of the TRAC-AYA intervention with a total of 50 participants (25 per condition).

Participants in the RCT will be enrolled in the study for a total of 10 weeks, whether they are in the intervention or control group. If participants are unable to complete monitoring or intervention tasks within the initial 4-week period, they will be given up to 6 weeks to complete the tasks before being considered noncompleters. The delayed post-test is delivered 4 weeks after completion of all monitoring/intervention tasks at 10 weeks.

Intervention (Group A) participants will complete 4 intervention sessions on a weekly basis, conducted via phone or videoconference (HIPAA-compliant Zoom), according to participant preference. These sessions will be audio recorded. Participants will also complete daily self-monitoring of alcohol use using mobile surveys and breathalyzers for 6 weeks. Control (Group B) participants will receive educational materials regarding alcohol use and will complete mobile monitoring of alcohol use in the same manner as Group A for 6 weeks. All RCT participants will complete a baseline assessment survey upon enrollment, a follow-up survey once all intervention/monitoring tasks are completed at 6 weeks, and a qualitative exit interview which will be audio recorded. All RCT participants will also complete a delayed post-test assessment at 10 weeks, 4 weeks after they complete the follow-up survey.

The total estimated maximum time commitment for RCT Group A (Intervention) participants is 13 hours, 45 minutes. The total estimated maximum time commitment for RCT Group B (Control) participants is 10 hours, 45 minutes.

All RCT participants will receive up to \$315 in Amazon e-gift cards for their participation.

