**RCT Data Collection:** For Group A (Intervention) participants only, a brief treatment expectations questionnaire assessing their attitudes toward the intervention will be administered. Additionally, after each counseling session, Group A participants will complete a short intervention session rating questionnaire. All counseling sessions will be audio recorded in order to provide supervision and fidelity checks for the interventionist. Both Group A and Group B (Control) will complete surveys assessing daily alcohol intake each morning and report blood alcohol content (via breathalyzer readings uploaded to REDCap) each evening until they have completed 42 total days of monitoring. In the unlikely event that participants are not able to upload their breathalyzer reading to REDCap, they will text a screenshot of their reading to the study coordinator on a study cell phone who will upload the reading to REDCap on the participant's behalf. Readings will be deleted from the study cell phone immediately after they are uploaded into REDCap. After all intervention/monitoring tasks are completed at 6 weeks, both groups will complete a follow-up questionnaire, which may be done in-person, online via REDCap, via phone, or via mail per participant preference. The follow-up questionnaire matches the initial baseline questionnaire, with additional questions about satisfaction with the intervention being shown to Group A (Intervention). All RCT participants will also complete a 20-30 minute semi-structured exit interview after completing the follow-up questionnaire. This interview will ask about perceptions of monitoring technology, perceived effects of monitoring, need for additional support, and suggestions for improvement. In addition to these, Group A (Intervention) participants will be asked questions regarding overall satisfaction with the TRAC program, reactions to session content, length, and components. The study coordinator will conduct the interviews. Interviews will be audio recorded and transcribed using a transcription service. Finally, 4 weeks after participants complete the follow-up survey, RCT participants will complete the delayed post-test survey at 10 weeks. This final data collection instrument matches the follow-up survey, but will not contain questions relating to satisfaction with the TRAC program. Participants may complete the delayed post-test in-person, online via REDCap, via phone, or via mail per participant preference.

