**Documenting/Reporting Adverse Events:** This protocol presents minimal risks to the subjects and adverse events are not anticipated. In the unlikely event that such events occur, serious and unanticipated and related adverse events will be reported in writing within 48 hours to the IRB and any appropriate funding and regulatory agencies. For the current study, the following individuals and agencies will be notified by the PI via e-mail within 5 days of the event occurring: the University of Kentucky IRB, the funding agency, and relevant collaborating organizations. [name] and [name] will review any adverse events that occur and evaluate their severity. Based on this review, we will determine if any changes to the protocol are required and will speak with the IRB if necessary.

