## Data and Safety Monitoring

The IRB requires review and approval of data and safety monitoring plans for greater than minimal risk research or NIH-funded/FDA-regulated clinical investigations.

- If you are conducting greater than minimal risk research, or your clinical investigation is NIH-funded, describe your Data and Safety Monitoring Plan (DSMP). [Click here for additional guidance on developing a Data and Safety Monitoring Plan](#).
- If this is a non-sponsored investigator-initiated protocol considered greater than minimal risk research, and if you are planning on using a Data and Safety Monitoring Board (DSMB) as part of your DSMP, [click here for additional guidance](#) for information to include with your IRB application.

Several mechanisms for monitoring the occurrence of adverse events will be employed. The study coordinator will oversee day-to-day monitoring of the study activities and will have daily contact with the principal investigator. There will be ongoing communication among the research team. This will be facilitated by: 1) weekly meetings with project staff and investigators to discuss study progress, reactions to the intervention, and any adverse events; 2) supervision of the study interventionist and study coordinator; and 3) the principal investigators will monitor the audiotaped intervention sessions. For medical adverse events, survivors will contact their oncology care team, primary care team, or emergency medical services as they would in routine care.

The study interventionist will receive training from [name] (MPI), a clinical psychologist, on how to effectively communicate via telephone and assess for actual or potential adverse psychological reactions. For patients who exhibit excessive or worrisome emotional reactions, the interventionist or MPI will follow-up with the patient by telephone within 24 hours and 1 week of the session to ensure that these survivors get adequate mental health care.

To protect privacy, all study databases will be password-protected and accessed only by study personnel.

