**Plans for Assuring Data Accuracy and Protocol Compliance:** Survey data will be collected via mail, in-person, and online through REDCap. All patient-reported and medical record extracted data will be stored in REDCap, a secure electronic data capture system offered by the University of Kentucky Center for Clinical and Translation Science (CCTS). REDCap provides a real-time record of any changes made to data, including which study team member made the change. REDCap can export data into SPSS and SAS for data analysis and run basic descriptive statistic reports. [name] will download the REDCap data and examine it for errors after the first 5 survivors have enrolled to check for errors and data problems. We will perform logic and range checks. Patient-reported data and medical record data entered by the study coordinator in REDCap will be examined for accuracy. To protect confidentiality, participants will be assigned a unique study identification number. All identifying information will be stored in separate electronic files. Protocol compliance will be monitored and discussed at weekly team meetings. Prior to implementing the intervention, all study personnel will undergo extensive training by the MPIs. To ensure standardized protocol delivery, both exit interviews and intervention sessions will be audiorecorded. These will be reviewed and corrective feedback will be provided.

In addition to these procedures, the UK Markey Cancer Center Protocol Review Monitoring Committee will monitor the study for accrual, scientific progress, data quality, and ethical conduct.

**Potential Adverse Events:** Potential adverse events include negative emotional responses following intervention sessions or assessments, or increased substance use. [name] current pilot study with veterans living with HIV/AIDS has not shown adverse psychological reactions to this intervention.

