**Plans for Assuring Compliance with Adverse Event Reporting:** All survivors will be provided with a study telephone number to call. The call line will be staffed during normal business hours (8:00 am to 5:00 pm) and have voicemail for after business hours. The study coordinator or other designated study staff will contact the survivor within 24 hours of a voicemail. All study staff will be trained and provided with a written protocol that instructs them to complete an electronic adverse event report and immediately send it to the MPIs for follow-up. All severe adverse events will be reported to the Institutional Review Board by the MPIs within 24 hours. The MPIs will also report all adverse events to the Institutional Review Board on an annual basis. In addition, all adverse events are reported to the NIH as part of the annual progress reports. The MPIs are responsible for contacting the National Cancer Institute grant program director in the event that any action resulting in temporary or permanent suspension of the trial occurs.

**Data Safety Monitoring Board:** In accordance with Markey Cancer Center's Institutional Data and Safety Monitoring Plan, the trial will be reviewed and monitored at least annually by the Markey Cancer Center Data and Safety Monitoring Committee (MCC DSMC), a key component of the Quality Assurance process for protocols being conducted at the University of Kentucky Markey Cancer Center. The MCC DSMC conducts real-time data monitoring and safety review of all trials. Through this process, the MCC DSMC also assesses the continuing validity and scientific merit of the trial. The MCC DSMC will review the trial as determined by the MCC Protocol Review and Monitoring Committee (PRMC). The MCC DSMC will monitor: Adverse Event Analysis, Serious Adverse Events, Protocol Deviations, Accrual, and when applicable, MCC Audit Committee Reports, previous reviews by the DSMC, suggested actions by other committees (e.g., IRB), and other parameters and outcomes as determined by the DSMC. The MCC DSMC can amend, temporarily suspend, or terminate the trial based upon patient safety or compliance concerns. Given the level of risk, as well as oversight by the UK Markey Cancer Center and study consultant review and role ([name]), we will not be forming an outside Data Safety Monitoring Board.

[Back to Top](#)

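### Active detection of adverse emotional reactions runs through sessions that only TRAC receives, so counts of recorded adverse events are not comparable between arms

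*Combined protocol and SAP*

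**What the plan says.** The Data and Safety Monitoring section lists what could go wrong: "Potential adverse events include negative emotional responses following intervention sessions or assessments, or increased substance use". Among its monitoring mechanisms, "the principal investigators will monitor the audiotaped intervention sessions". The interventionist is trained to "assess for actual or potential adverse psychological reactions", and for a worrying reaction "the interventionist or MPI will follow-up with the patient by telephone within 24 hours and 1 week of the session".

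The sessions belong to one arm. Under Study Procedures: Randomized Controlled Trial, "Intervention (Group A) participants will complete 4 intervention sessions on a weekly basis"; controls receive educational materials and the same monitoring. For adverse-event reporting by everyone, "All survivors will be provided with a study telephone number to call". Medical events are left to the participant's usual care contacts.

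Measurement of drinking is the same in both arms. Under RCT Data Collection, "Both Group A and Group B (Control) will complete surveys assessing daily alcohol intake each morning", with a breathalyzer reading each evening, until 42 days are complete. The baseline questionnaire covers alcohol, tobacco and other substances. It is repeated at week 6 and, in matching form, at week 10. The SAP (1.4.2.2) compares pre-post change in alcohol use between arms by t-test. It has no section on harms.

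**The concern.** A named adverse event should have the same chance of being recorded in either arm. Here one arm has a trained person looking for reactions at four scheduled points, with investigators listening to the recordings. The other arm mostly has to volunteer the information. If true risk were equal, TRAC would tend to show more recorded events.

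Two readers of those counts could be misled. The institutional monitoring committee has adverse-event analysis on its list of items to review. The team planning the definitive trial will want to say something about tolerability. There is also a loss within the control arm: the Study Design section accepts that monitoring alone may change behaviour, and the supplied text gives no rule by which a control participant whose drinking rises would be logged as having an adverse event, although the data arrive daily.

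**Working it through.** The plan states no event rate or harms calculation, so there is no figure to reproduce. The check is a listing of each route by arm.

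| Route (section) | TRAC | Control | Stated as a way of finding adverse events? |
|---|---|---|---|
| Interventionist assesses reactions (Data and Safety Monitoring) | 4 sessions | none | Yes |
| Investigators review session recordings (same) | yes | none | Yes |
| Study telephone line (same) | yes | yes | Yes, if the participant calls |
| Usual care for medical events (same) | yes | yes | Yes, if the participant makes contact |
| Morning survey and evening breathalyzer (RCT Data Collection) | 42 × 2 = 84 entries | 84 entries | No rule stated |
| Questionnaires at baseline, week 6, week 10 (RCT Enrollment, RCT Data Collection) | yes | yes | No rule stated |
| Exit interview after the week-6 questionnaire | yes | yes | Not stated; recordings are reviewed for standardized delivery |
| Trained staff, written reporting protocol, weekly meetings, emergency protocol | yes | yes | They handle and report events once known |

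**Contact.** With the protocol's 25 per arm, planned sessions are 25 × 4 = 100 in TRAC and 25 × 0 = 0 in control. Maximum participant time differs by 13 h 45 min − 10 h 45 min = 180 minutes.

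**Which events are affected.** Reactions to sessions can occur only in TRAC, so finding them only there is not a bias. Reactions to assessments, and increased substance use, can occur in both arms.

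**Direction.** Expected recorded events per arm = n × p × s, where p is the true risk and s the probability that an event is recorded. With n and p equal, the spurious difference is n × p × (s_TRAC − s_control), which is positive whenever sessions raise detection.

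**Illustration.** All values of p and s below are assumptions. They concern emotional reactions possible in both arms, not measured alcohol use. Take n = 25, s_TRAC = 0.9 and s_control = 0.9, 0.6 or 0.3:
- p = 10%: 25 × 0.10 × 0.9 = 2.25 recorded in TRAC, against 2.25, 1.5 or 0.75 in control.
- p = 20%: 4.5 against 4.5, 3.0 or 1.5.
- p = 30%: 6.75 against 6.75, 4.5 or 2.25.

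The spurious excess therefore runs from 0 (equal detection) to 4.5 events.

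**What 25 per arm could show with equal detection.** Using the normal approximation, two-sided 5%, for 10% against 30%: z = [0.20 − 1.96 × √(2 × 0.2 × 0.8/25)] / √((0.09 + 0.21)/25) = (0.20 − 0.222)/0.110 ≈ −0.20, so power is about 42%. For 20% against 40% it is about 34%. Any harms comparison is descriptive.

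**SAP.** Sections 1.1 to 1.4.2.3 cover the enrollment hypothesis, sample size, populations, qualitative coding, feasibility, preliminary outcomes and fidelity. The t-tests in 1.4.2.2 compare mean change, and an average fall can coexist with individual worsening.

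**The case against.** The strongest reply is that the event of most interest, increased drinking, is captured identically in both arms and compared in the SAP. That stands. A reader might infer that harms cannot be compared at all, or that any statement about TRAC not increasing drinking would rest on a biased comparison. The documents do not support either: the surveys, breathalyzer readings and questionnaires do not depend on sessions. What remains is that measuring a quantity is different from identifying an adverse event from it.

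Second, controls are not without trained contact. All study staff are trained to file adverse-event reports, weekly meetings cover adverse events, and the emergency protocol and emergency contacts apply to both arms. This stands, and it is why control events may be under-recorded rather than certain to be missed. But these provisions act mainly after an event has come to light.

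Third, several operating documents are cited but not supplied, among them the written adverse-event protocol, the emergency protocol, the detailed protocol and the coordinator manual. A screening rule could be in one of them. One can say only that the supplied text states none.

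Fourth, this is a minimal-risk feasibility pilot with no planned between-arm harms test. That limits the weight of the point without removing it.

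A reader might also see a contradiction with the statement in Records, Privacy, and Confidentiality that "This protocol presents minimal risks to the subjects and adverse events are not anticipated". There is none: listing what could happen is compatible with not expecting it.

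**Conclusion.** The point holds as a matter of unequal recording. Active detection of emotional reactions is tied to four sessions that only TRAC receives. Before the week-6 questionnaire and exit interview, control-arm events rest mainly on participants calling in. Counts of recorded adverse events are therefore not comparable between arms, and the likely direction is against TRAC. The amount is unknown; the illustrated excess of 0 to 4.5 events in 25 depends wholly on assumed risks and detection probabilities. The conclusion does not extend to average change in alcohol use, which is collected symmetrically, or to the feasibility outcomes. It assumes that no unsupplied procedure already screens the daily data. The SAP's total of 40 differs from the protocol's 50, but this does not affect the argument. This is an inexpensive improvement worth making, not a threat to the pilot's main aim.

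**What to change.** 1. State that increased substance use is identified as an adverse event in both arms by one rule. The investigators set it without reference to arm. It is applied to the daily surveys, breathalyzer readings and baseline, follow-up and delayed post-test questionnaires already collected, and events are logged on the existing electronic form. The threshold and any clinical response are for the investigators to decide.
2. Add a short harms section to the SAP: a descriptive table by arm and by source (systematic, session-detected, spontaneous). Base any between-arm statement only on the systematically collected events.
3. The informed consent section says that enrollment is closed. Where data collection is still open, or otherwise in the planned definitive trial, add one identical adverse-event question to the follow-up and delayed post-test surveys in both arms.

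The first two items use data already in REDCap and existing staff. The cost is that more events will be logged. Some controls may also receive extra contact, which slightly alters a comparator meant to be education and monitoring alone.

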## Future Use and Sharing of Material (e.g., Data/Specimens/Information)

If the material collected for this study will be used by members of the research team or shared with other researchers for future studies,

please address the following.

- list the biological specimens and/or information that will be kept
- briefly describe the types, categories and/or purposes of the future research
- describe any risks of the additional use
- describe privacy/confidentiality protections that will be put into place
- describe the period of time specimens/information may be used
- describe procedures for sharing specimens/information with secondary researchers
- describe the process for, and limitations to, withdrawal of specimens/data

Data obtained as part of this study (survey data, recordings from interviews) will be stored, used, and shared for future research. All identifiable information (e.g., name, medical record number, or date of birth) will be removed from the information or samples collected in this study. This means that no link or code to the participant's identity will be kept. After all identifiers have been removed, the information may be used for future research or shared with other researchers without additional informed consent. Once participants give their permission to have their de-identified information stored, they will be available indefinitely and cannot be removed due to the inability to identify them. These data will be stored for up to 6 years following study closure.

Researchers can use the stored information to learn more about alcohol use in survivors of adolescent and young adult cancer, or research additional scientific questions.

There are no risks of additional use, however there is a risk of a breach of confidentiality. The research team will take all precautions to protect against this. Please see the 'Records, Privacy, and Confidentiality' section of this protocol for details of how we will keep participant information private and secure.

Are you recruiting or expect to enroll **Non-English Speaking Subjects or Subjects from a Foreign Culture?** (does not include short form use for incidentally encountered non-English subjects)

Yes  No

—Non-English Speaking Subjects or Subjects from a Foreign Culture—————

#### **Recruitment and Consent:**

Describe how information about the study will be communicated to potential subjects appropriate for their culture, and if necessary, how new information about the research may be relayed to subjects during the study.

When recruiting Non-English-speaking subjects, provide a consent document in the subject's primary language. After saving this section, attach both the English and translated consent documents in the "Informed Consent" section.

#### **Cultural and Language Consultants:**

The PI is required to identify someone who is willing to serve as the cultural consultant to the IRB.

- This person should be familiar with the culture of the subject population and/or be able to verify that translated documents are the equivalent of the English version of documents submitted.
- The consultant should not be involved with the study or have any interest in its IRB approval.
- Please include the name, address, telephone number, and email of the person who agrees to be the cultural consultant for your study.
- ORI staff will facilitate the review process with your consultant. Please do not ask them to review your protocol separately.

For more details, see the IRB Application Instructions on [Research Involving Non-English Speaking Subjects or Subjects from a Foreign Culture](#).

